Up to 27 subjects are planned to be entered in this trial. Cohort 1 was planned to have 6 subjects, but enrollment was stopped after 5 subjects when brequinar PK and DHO results became available. These results led to study design changes as described here. The sixth subject will not be enrolled in Cohort 1.

Cohort 2 will enroll approximately 6 subjects, followed by an expansion cohort of approximately 15 subjects. All subjects in Cohort 2 will start with a 500 mg/m² dose once-weekly. Brequinar PK and DHO samples will be obtained for these subjects in Week 1 and results used to make decisions about the Week 2 once-weekly dose. Brequinar PK and DHO samples will also be obtained for Week 2 and the results used to make decisions about Week 3 dose frequency (once or twice-weekly) and the dose. The dose will be adjusted for each subject to meet the twice-weekly brequinar PK and 72-hour DHO criteria, and the Week 2 procedures may be repeated if needed until the twice-weekly dose is found.

After both the brequinar PK and 72-hour DHO level meet criteria described in the Individual Dose Adjustment Guidelines as described in Protocol Section 8.5, a subject may move to twice-weekly dosing on a continuing basis as tolerated. The twice-weekly dose may be further adjusted using 84-hour DHO (trough ~ 84 hours after dosing) criteria, also described in the Guidelines for Individual Dose Adjustment.

Dosing will continue up to 12 months in the absence of unacceptable toxicity or disease progression, or may be discontinued with Sponsor consent after completing at least 6 weeks of dosing.

B. Study Population

Up to 27 subjects 18 years or older with relapsed/refractory AML by World Health Organization (WHO) classification who have exhausted available therapy and who meet all inclusion/exclusion criteria will be enrolled at 3- 6 sites in the United States.

C. Sample Size Predictions

Formal sample size calculations are not applicable to this phase 1b/2a dose-adjustment and expansion study.

V. General Analytical Considerations

All analyses of safety and anti-leukemic activity for this open-label, early-phase study will be descriptive in nature and presented by dose group and overall, as appropriate, for dose-adjustment and expansion phases.

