A summary table will be constructed to display the anatomical main class (1st level) of each coded medication and, within that, the pharmacological subgroup (3rd level). It will include counts and percentages of subjects who reported using at least one medication in each pharmacological subgroup.

L. Blood Transfusions

Any blood transfusions received up to eight weeks prior to Cycle 1 Day 1 (baseline event), and during the study, including start and end dates, blood product, total number of units received, and reason for transfusion will be listed and summarized.

VIII. Efficacy Analyses

The secondary objectives of the study will be addressed using the Efficacy Analysis Set of subjects.

A. Disease Response

As per criteria defined in the ELN Guidelines by [Dohner et al, 2017](#), disease response will be assessed at screening and post-screening visits and included in a data listing. Additionally, anti-leukemic activity will be evaluated as per the following outcomes:

Response Rates: The distribution of best overall response (BOR) of CR, CRi, CRh, MLFS, or PR will be summarized by treatment cohort and overall. Point estimates with two-sided exact 95% and 90% confidence intervals (CIs) will be included for:

- Overall response rate (ORR) defined as the proportion of subjects who achieve a best overall response of CR, CRi, CRh, MLFS, or PR.
- Complete remission rate defined as the proportion of subjects who achieve a best overall response of CR.
- Complete remission with incomplete hematologic recovery rate defined as the proportion of subjects who achieve a best overall response of CRi.
- Complete remission with partial hematological recovery rate defined as the proportion subjects who achieve a best overall response of CRh.
- Morphological leukemia-free state rate defined as the proportion of subjects who achieve a best overall response of MLFS.
- Partial remission rate defined as the proportion of subjects who achieve best overall response of PR.

Additional information on precise definitions of these response categories can be found in Section 10.3 of the protocol.

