Duration of Response: Duration of response will be defined as the time from the first occurrence of a qualifying response of CR, CRi, CRh, MLFS, or PR, to the date when progressive disease is objectively documented or death due to any cause, whichever occurs earlier. Following the qualifying response, subjects who are alive without disease progression will be right-censored at the date of last disease evaluation. A Kaplan-Meier graph will be plotted by treatment group and estimates of median duration with associated 95% CIs will be reported.

Event-free Survival (EFS): Event-free survival will be determined from the first dose of brequinar to the date of relapse ($\geq 5\%$ bone marrow blasts, reappearance of blasts in blood, or development of extramedullary disease), disease progression, or death, whichever occurs first. Subjects who do not experience any of the three events will be right-censored at the latter date of disease evaluation or bone marrow sampling. A Kaplan-Meier graph will be plotted for time to the composite outcome by treatment group, and the estimate of medial survival time with 95% CI will be summarized.

Overall Survival (OS): Overall survival will be calculated as the time from the first dose of study drug to the date of death or right-censoring at the date of last subject contact. Median time to OS, with 95% CI, will be summarized and displayed graphically by treatment group using the Kaplan-Meier method.

B. Clinical Benefit

In addition to ORR, this study will examine clinical benefit to subjects. By treatment group, a summary table will report counts and percent of transfusion-dependent subjects at baseline who, in the absence of progression, CR or PR, and independent of marrow response, achieve one of the following:

- Erythroid response: Transfusion Independence (TI) for 8 or more weeks for subjects requiring at least 4 units of packed red blood cell transfusions in the previous 8 weeks. Only red blood cell transfusions given based on physician's judgment for a pretreatment hemoglobin (Hgb) of ≤ 8.5 g/dL will count in the red blood cell TI response evaluation.
- Platelet response: TI for subjects requiring a minimum of 4 platelet transfusions in the previous 8 weeks.

IX. Pharmacokinetic Analyses

The plasma PK of brequinar and DHO will be characterized using non-compartmental analysis. Where possible, the following standard PK parameters will be calculated:

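### The SAP's rules for best response, duration of response and EFS have no cut at new anti-leukemic therapy or transplant, so any disease assessment made after it would count as a brequinar outcome

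*SAP*

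**What the plan says.** All the rules at issue stand in SAP section VIII.A.

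- **Response.** On timing, the SAP says that "disease response will be assessed at screening and post-screening visits and included in a data listing". ORR is "the proportion of subjects who achieve a best overall response of CR, CRi, CRh, MLFS, or PR". No last eligible assessment is named.
- **DOR.** It runs from the first qualifying response "to the date when progressive disease is objectively documented or death due to any cause, whichever occurs earlier". Otherwise: "Following the qualifying response, subjects who are alive without disease progression will be right-censored at the date of last disease evaluation".
- **EFS.** It runs from first dose to relapse, "disease progression, or death, whichever occurs first". Otherwise: "Subjects who do not experience any of the three events will be right-censored at the latter date of disease evaluation or bone marrow sampling".
- **OS.** It runs to "the date of death or right-censoring at the date of last subject contact". The point does not touch OS.

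Two other sections matter. Under IV.A (Design Overview), dosing "may be discontinued with Sponsor consent after completing at least 6 weeks of dosing". The reasons for discontinuation in VI.B (Disposition) include adverse event and a decision by the physician or sponsor. A subject can therefore leave brequinar without having progressed.

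**The concern.** The DOR and EFS rules are complete enough to program, and a programmer following them would use every later disease assessment in the database. Suppose a subject has not responded, stops brequinar after week 6 without progression, starts another drug and is then found in CR. By the text this subject has a BOR of CR, enters the DOR analysis and is event-free. A brequinar responder who goes to transplant while in remission has the post-transplant remission counted in DOR.

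The trial has a single arm and small groups, so no comparator shows how much of an outcome belongs to the next treatment. If the handling is left open until the analysis of an open-label study, it can also be settled once the results are known.

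**Working it through.** **1. Search for a cut-off.** The SAP states no figure on this point that could be reproduced, so the first check is of the text.

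| Outcome | Ends at | Otherwise | Cut at new therapy or transplant |
|---|---|---|---|
| BOR/ORR | no closing date | not applicable | none |
| DOR | progression or death | last disease evaluation | none |
| EFS | relapse, progression or death | later of disease evaluation or marrow sampling | none |

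Neither V.D (Missing Data) nor VI.B supplies a rule. VIII.A refers to protocol section 10.3 only for the definitions of the response categories. For safety, VII.D does set a window after the last dose (30 days for treatment-emergent events); efficacy has no counterpart.

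**2. ORR.** BOR is the best of the eligible assessments, and adding assessments to a set cannot make its best member worse. The effect on ORR is therefore zero or upward.

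Inputs from IV.A: Cohort 1 stopped at 5, Cohort 2 has about 6 and the expansion cohort about 15, so n = 5 + 6 + 15 = 26. I assume that all are in the Efficacy Analysis Set; with fewer, each case weighs more. One response credited from later therapy adds 1/n:

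- overall: 1/26 = 3.8 points
- expansion cohort: 1/15 = 6.7 points
- Cohort 2: 1/6 = 16.7 points
- Cohort 1: 1/5 = 20 points

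Exact (Clopper-Pearson) two-sided 95% intervals, the type the SAP plans, use these limits for x responders out of n: lower = the 2.5% quantile of Beta(x, n − x + 1), or 0 if x = 0; upper = the 97.5% quantile of Beta(x + 1, n − x).

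| True count | Estimate (95% CI) | With one credited case | Estimate (95% CI) |
|---|---|---|---|
| 0/26 | 0% (0 to 13.2) | 1/26 | 3.8% (0.1 to 19.6) |
| 2/26 | 7.7% (0.9 to 25.1) | 3/26 | 11.5% (2.4 to 30.2) |
| 2/15 | 13.3% (1.7 to 40.5) | 3/15 | 20.0% (4.3 to 48.1) |

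The starting counts are illustrative. For 0/26 the upper limit reduces to 1 − 0.025^(1/26) = 0.132.

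**3. DOR.** The SAP gives no rate of subsequent therapy, so this step rests on assumed inputs. Take an exponential DOR with a median of 3.0 months on brequinar, hazard λ = ln 2 / 3 = 0.231 per month. Let a fraction f of responders start new therapy before an event, at rate λf/(1 − f), unrelated to prognosis. After the switch, multiply the hazard by m and follow to the event. Medians in months from 400,000 simulated subjects per setting:

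| f | m = 0.25 | m = 0.5 | m = 1 | m = 2 |
|---|---|---|---|---|
| 10% | 3.10 | 3.06 | 3.00 | 2.92 |
| 20% | 3.26 | 3.15 | 3.00 | 2.82 |
| 30% | 3.47 | 3.26 | 3.00 | 2.71 |
| 40% | 3.80 | 3.41 | 3.00 | 2.60 |

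Following subjects through later therapy lengthens the reported median if that therapy helps and shortens it if the later hazard is higher. Over these settings it reads 2.60 to 3.80 months against 3.0. EFS also counts progression and death after later therapy as events, so the same reasoning applies there.

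**The case against.** The SAP is silent on subsequent therapy. A reader might infer that it directs disease follow-up through the next treatment, but no sentence says so. Whether evaluations continue after brequinar stops depends on the visit schedule, which a SAP may leave to the protocol. If they stop with treatment, censoring at the last evaluation already falls near the proposed cut, and little is miscredited. Eligible subjects have exhausted available therapy, which makes a later response less likely. Those who stop for progression already have an EFS event. All of this stands, and it limits the size.

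A reader might also infer that all three outcomes can only move in brequinar's favour. That holds for ORR alone. Death from any cause ends DOR, and death also ends EFS, so deaths after salvage treatment or transplant count against the drug. Nor are these the only results on anti-leukemic activity: VIII also has OS and transfusion response.

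Following DOR and EFS regardless of later therapy is a legitimate treatment-policy choice. Censoring at new therapy has its own weakness, because subjects who switch may differ in prognosis from those who do not. This supports declaring the present DOR and EFS rules rather than replacing them. It does not help BOR, where a response first reached on another treatment is not a response to brequinar.

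Finally, the analyses are descriptive and the primary objective is safety and DHODH inhibition, so no test or power depends on the rule. That bears on the weight of the point, but the stated rule can still give a wrong ORR.

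**Conclusion.** The point holds as a missing cut-off. Event and censoring rules belong in a SAP. This one sets them out without the case of new therapy, although its own text allows subjects to leave brequinar before progression. Applied literally, the rules credit to brequinar any outcome assessed after the next treatment.

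For ORR the error has one direction: each case adds 3.8 points among 26 subjects and up to 20 points in the group of 5. For DOR and EFS the direction is open, and the range in months above is only an illustration. How many subjects would be affected cannot be derived from the SAP; the number is zero if no disease evaluation takes place after new therapy starts. The documents do not support a claim that the plan is biased towards brequinar throughout. The change should be made before database lock.

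**What to change.** In SAP section VIII.A:

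1. Count towards BOR and ORR, and as the qualifying response for DOR, only responses documented before the start of any new anti-leukemic therapy, including transplant. The denominator stays the Efficacy Analysis Set.
2. Keep the present DOR and EFS rules and declare that they follow subjects regardless of later therapy. Add a sensitivity analysis of each, censored at the last disease evaluation before new therapy. Note that this censoring may be informative and can move the estimate in either direction.
3. List the start date and type of the first subsequent therapy beside BOR, DOR and EFS.

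OS stays as written.

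The cost is a few sentences, one derived date and two further Kaplan-Meier tables. Section VII.K already has treatments during the study recorded in the eCRF, with start date if known. The SAP does not say whether therapy begun after a subject leaves the study is captured, so that should be checked. ORR may come out slightly lower.

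### Duration of response and event-free survival use different censoring dates and different event lists for the same responder, so the end of a response is not uniquely defined

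*SAP*

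**What the plan says.** All of this is in SAP Section VIII.A.

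- **DOR, event:** from the first qualifying response "to the date when progressive disease is objectively documented or death due to any cause, whichever occurs earlier". Relapse is not named.
- **DOR, censoring:** "subjects who are alive without disease progression will be right-censored at the date of last disease evaluation".
- **EFS, event:** relapse, progression or death. Relapse is spelled out as at least 5% "bone marrow blasts, reappearance of blasts in blood, or development of extramedullary disease), disease progression, or death, whichever occurs first".
- **EFS, censoring:** subjects with none of these "will be right-censored at the latter date of disease evaluation or bone marrow sampling".
- **Disease evaluation:** by the ELN criteria, "disease response will be assessed at screening and post-screening visits and included in a data listing". The SAP does not say whether a marrow sample is part of a disease evaluation or carries its own date. Marrow blast percentages are listed and summarised separately, in Section VII.F.
- **Estimator for DOR:** "A Kaplan-Meier graph will be plotted by treatment group and estimates of median duration with associated 95% CIs will be reported".
- **Size:** "Up to 27 subjects are planned to be entered in this trial" (Section IV.A). No response rate or expected duration is given, and Section V makes the analyses descriptive.

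**The concern.** Two adjacent paragraphs give different end-of-follow-up rules for the same state, alive without progression. The EFS rule makes sense only if a marrow date can differ from a disease evaluation date, so the mismatch is not merely verbal.

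The statistical worry is asymmetry. Suppose a marrow taken after the last disease evaluation can document the end of a response. A bad result is then an event on its own date. A clean result adds no follow-up, and the subject leaves the DOR risk set at the earlier evaluation. Follow-up then depends on the result of the sample, and the Kaplan-Meier curve is pulled down.

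The event lists raise the opposite worry. If a responder relapses in the marrow and this is not recorded as progressive disease, DOR continues while EFS has ended. Two programmers could derive different DOR dates from the same record. With few responders, one or two dates can decide whether a median is reached.

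**Working it through.** The SAP states no expected DOR, event count or power, so there is no planned figure to reproduce. The check is of direction and size. Every time, schedule and fraction below is an assumption.

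**1. Five responders, by hand.** D loses response at week 8. A loses it on a week-12 marrow. B and C have clean week-12 marrows but a last disease evaluation at week 8. E is clean at week 16. Kaplan-Meier: S(t) is the product of (1 − events/at risk).

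| Reading | Week 8 | Week 12 | S(12) | Median |
|---|---|---|---|---|
| Marrow can end DOR; censor at last evaluation | 1 of 5 | 1 of 2 | 0.80 × 0.50 = 0.40 | 12 weeks |
| Marrow can end DOR; censor at later date | 1 of 5 | 1 of 4 | 0.80 × 0.75 = 0.60 | not reached |
| A's marrow relapse is not a DOR event | 1 of 5 | none | 0.80 | not reached |

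The first two rows show the shortening, and the third shows the lengthening when relapse is left out. The example is built to make the effect visible.

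**2. A milder example.** Events at weeks 10 and 20, and subjects censored at weeks 16 and 24. A fifth subject has a last evaluation at week 8 and a clean marrow at week 12.

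- Censor at week 8: S(10) = 1 − 1/4 = 0.75; S(20) = 0.75 × 1/2 = 0.375.
- Censor at week 12: S(10) = 1 − 1/5 = 0.80; S(20) = 0.80 × 1/2 = 0.40.

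**3. Simulation over regular schedules.** 20,000 responders, exponential time to loss of response, follow-up uniform over 8 to 52 weeks. Each cell gives S(24), then the median in weeks. The true S(24) is 0.5^(24/12) = 0.250 or 0.5^(24/26) = 0.527.

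| Evaluations / marrows | True median | Marrow ends DOR, censor at evaluation | Marrow ends DOR, censor at later date | Evaluations only, for events and censoring |
|---|---|---|---|---|
| 4-weekly / same dates | 12 | 0.249; 16 | 0.249; 16 | 0.249; 16 |
| | 26 | 0.528; 28 | 0.528; 28 | 0.528; 28 |
| 4-weekly / 4-weekly, offset 2 weeks | 12 | 0.244; 12 | 0.250; 14 | 0.250; 16 |
| | 26 | 0.516; 26 | 0.523; 26 | 0.524; 28 |
| 4-weekly / 8-weekly from week 6 | 12 | 0.251; 14 | 0.255; 14 | 0.254; 16 |
| | 26 | 0.528; 28 | 0.531; 28 | 0.532; 28 |
| 8-weekly / 8-weekly from week 4 | 12 | 0.237; 12 | 0.250; 12 | 0.250; 16 |
| | 26 | 0.517; 28 | 0.531; 28 | 0.530; 32 |
| 12-weekly / 4-weekly | 12 | 0.223; 12 | 0.251; 16 | 0.250; 24 |
| | 26 | 0.496; 24 | 0.527; 28 | 0.526; 36 |

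The gap between the first two rules is zero when dates coincide, 0.003 to 0.014 in the three schedules with 4- or 8-weekly evaluations and separate marrow dates, and about 0.03 in the last. The median is 0 to 4 weeks shorter. In the last column a marrow finding does not itself end DOR: S(24) shows no downward bias, and the median is the same or later because detection waits for the next evaluation.

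**4. Sensitivity to short follow-up.** True median 16 weeks, 4-weekly visits, and a final visit that is marrow-only in a fraction q of subjects.

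- Follow-up ending at weeks 4 to 24: S(24) is about 0.35 under the later-date rule, against about 0.32 (q = 25%) and 0.27 (q = 50%) when censoring at the evaluation.
- Follow-up ending at weeks 4 to 52: about 0.354, against 0.345 (q = 25%) and 0.338 (q = 50%).
- Five responders, short follow-up: the reported median differs between the two rules in roughly 6 to 8% (q = 25%) and 12 to 13% (q = 50%) of simulated trials.

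**The case against.** A reader might infer that DOR is simply biased short. The SAP does not support that. DOR ends at objectively documented progressive disease or death, and the marrow-blast criterion belongs to relapse in the EFS paragraph. Using it to end DOR imports an EFS event.

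The shortening also needs one kind of sample to have two statuses. If a bad marrow documents progression, it arguably served as a disease evaluation. A clean one then serves equally, its date is the censoring date, and the bias disappears. The SAP refers to protocol Section 10.3 for the response definitions, which is not at hand, so this cannot be settled here. The larger effects come from assumed short follow-up and a high share of marrow-only final visits, whereas Section IV.A allows dosing for up to 12 months. No test or decision rests on DOR.

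All of that stands against an unconditional claim of bias. It does not remove the inconsistency. The SAP itself fixes both censoring rules, its EFS wording treats the two dates as able to differ, and it explains neither the different dates nor the different events.

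**Conclusion.** The concern holds as an inconsistency, with a bias whose direction is conditional. One responder can have two event-free end dates, and relapse ends EFS without being named as ending DOR.

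- If a marrow result can end DOR and a marrow date is not a disease evaluation, Kaplan-Meier DOR can be too short. The effect is small in most schedules tried: 0.003 to 0.014 at 24 weeks, about 0.03 with sparse evaluations, and larger only with short follow-up and many marrow-only final visits.
- If marrow and evaluation dates coincide, the censoring rules agree.
- If relapse does not end DOR, the omission tends to lengthen it.

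The SAP does not say how often a marrow follows the last disease evaluation, so every size above rests on assumption. Severity is low: a descriptive secondary endpoint, in responders only, in a trial of at most 27 subjects.

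**What to change.** In the Duration of Response paragraph of Section VIII.A:

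1. End DOR at the earliest of relapse (as defined for EFS), progressive disease and death.
2. Censor responders with none of these at the last disease evaluation or the last marrow sample, whichever is later.
3. Derive that date once and use it for EFS as well, correcting *latter* to *later* in the EFS paragraph.

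Steps 1 and 2 belong together. Moving only the censoring date, while a marrow relapse is not a DOR event, would credit time in which the DOR event was not assessed.

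The cost is a sentence or two of SAP text and reuse of a date already needed for EFS. There is a small downside: a marrow-only date credits event-free time when blood blasts or extramedullary disease may not have been checked. The EFS rule already accepts this.
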